Subjects will be delimited to patients with irritable bowel syndrome selected from the outpatient of national nutrition institute with the following criteria:

- Sixty six patients with irritable bowel syndrome of both genders.
- Their ages ranged from 20 to 45 years.
- Their Body mass index ranged from 30 to 34.9.
- Patients will be divided into 3 groups
 - **Group A:** Patients will receive moderate intensity continues training exercise program along with following Low fermentable, oligosaccharides, disaccharides, monosaccharides and polysaccharides diet plan (FODMAPs diet).
 - **Group B:** Patient will receive high intensity interval training exercise program along with following FODMAP diet plan.

- **Group C:** Patients will follow FODMAP diet plan only.
- Patients will be excluded if:
 - - Uncontrolled hypertension
 - - Gastrointestinal bleeding
 - - Colorectal cancer or any terminal diseases
 - - Communication disorders

Basic Assumptions:

It will be assumed that:

- 1) The primary medical assessment will be done to every participating patient who includes:
- 2) Complete medical history (personal, present and past)
- 3) All patients will stick to the program and will follow instructions.
- 4) All other factors which may influence the outcome such as noise and distraction will be controlled.

Hypothesis:

It will be hypothesized that there will be no significant difference between the moderate continuous versus high interval intensity training on gut dysbiosis and glucagon like peptide hormone in irritable bowel syndrome.

CHAPTER II

REVIEW OF LITERATURE

The human gastrointestinal (GI) tract represents one of the largest organ between the host, environmental factors and antigens in the human body. In an average life time, around 60 tonnes of food pass through the human GI tract, along with an abundance of microorganisms from the environment which impose a huge threat on gut integrity. The collection of bacteria, archaea and eukarya colonising the GI tract is termed the ‘gut microbiota’ and has co-evolved with the host over thousands of years to form an intricate and mutually beneficial relationship (**Thursby and Juge,2017**).

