Among humans, positive correlations were reported between bacterial diversity, butyrate-producing bacteria and cardiorespiratory fitness (VO₂max), and higher turnover of carbohydrates and proteins, and concentrations of short-chain fatty acids in athletes compared to sedentary controls. There is also growing evidence that physical activity status and exercise training may shape the gut microbiome (**Cataldi et al.,2022**).

Physical activity stimulates bacterial community richness by altering SCFAs-producing species, as well as favoring the colonization of health and athletic performance-promoting strains. The ability to promote a bacterial

composition capable of protecting the intestinal mucosa also it was found that the effects on gut microbiome seem to gradually disappear when the physical activity is no longer practiced (**Cataldi et al., 2022**).

Moderate aerobic exercise affects the intestinal system mainly through gut immune function gut barrier integrity through tight junction proteins expression and IgA production hypothalamic–pituitary–adrenal (HPA) axis stimulation which, in turn, affects enteric nervous system and intestinal transit time, as well as gut motility, intestinal pH and gut hormones release and bile acids metabolism within enterohepatic circulation (**Cella et al.,2021**).

High intensity interval training (HIIT) encompasses exercise prescriptions that are tailored to individual needs and can be used in most any exercise setting. This ability to adapt makes HIIT a valuable tool in the exercise programming of patients with a chronic disease. HIIT has a positive effect on the Bacteroidetes/Firmicutes ratio and also increased the alpha diversity in gut microbiota (**Denou et al.,2016**).

Chapter III

[figure not shown]
PATIENTS, MATERIALS AND METHODS

The current study is designed to compare between the effect of moderate continuous and high interval intensity training on gut dysbiosis and glucagon like peptide hormone in irritable bowel syndrome.

I. Patients:

This study will be carried out on sixty six irritable bowel syndrome patients of both sexes with an age range between twenty to forty five years. Patients will be recruited and practical work of the study will be carried out in national nutrition institute physiotherapy out clinic. Patient will be randomly assigned to three groups.

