To avoid type II error, sample size calculation is performed using G*POWER statistical software (version 3.1.9.2; Franz Faul, Universitat Kiel, Germany). To detect a large effect size of 0.4 with power of 80% and $\alpha=0.05$, the required sample size required for this study was $N=66$.

Ethical consideration:

- Approval of faculty ethical committee.
- The study procedure will be explained for all participants.
- Confidentiality will be assured.
- An informed consent will be taken from each subject prior to participation.

(Appendix I)

Criteria for the patient selection:

Inclusion criteria:

- 1) Patients will be selected with age range of 20 to 45 years of both genders.
- 2) Body mass index (BMI) will range from 30 to 34.9 kg\m².
- 3) Having more than one symptom for ROME IV for IBS diagnostic criteria **(Appendix II).**
- 4) Prediabetic with glycated hemoglobin HbA1c of 5.7 – 6.4.
- 5) Sedentary subjects with daily steps count less than five thousand steps measured by pedometer **(Prince et al.,2020).**

Exclusion criteria:

Patients with the following criteria will be excluded from the study:

- 1) Communication disorders
- 2) Gasterointestinal bleeding
- 3) Antibiotics or probiotics in the last 2 months
- 4) Recent surgeries in the last 6 months
- 5) Colorectal cancer or any terminal diseases
- 6) Fibromylgia or Multiple sclerosis
- 7) Palpable abdominal mass
- 8) Cardiovascular diseases

- 9) Active smokers
- 10) Musculoskeletal injuries that interfere with exercise program
- 11) Upper respiratory infections
- 12) Uncontrolled hypertension

Patients will be divided into 3 groups:

- **Group (A):** This group will include 22 patients with IBS. These patients will receive 40 minutes of MICT on the treadmill: 5 minutes of warm-up followed by 30 minutes of 65-75% of target heart rate ending with a 5 min cool-down period for 12 weeks along with following low FODMAP diet plan.
- **Group (B):** This group will include 22 patients with IBS. These patients will receive HIIT sessions consisting of a 30 minutes treadmill session a 5 minutes warm-up followed by 10 bouts of 1 minute at 90% of target heart rate interspersed by 10 bouts of 1 min of active recovery at 50% of target heart rate (totaling 20 min), and a 5 minutes cool-down period for 12 weeks along with following low FODMAP diet plan.
- **Group (C)** This group will include 22 patients with IBS. These patients will follow low FODMAP diet plan for 12 weeks

Materials and Methods

- **Evaluation**

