After collecting the consent forms, will be examined by the researcher for the inclusion and exclusion criteria. Each eligible patient (according to the consent form and examination) will participate in the study.

Group A

Patients will receive moderate intensity continuous training (MICT).

The program will be in form of: (Clark et al.,2020).

- **Frequency:** Moderate continues training will be scheduled 3 times per week for 12 weeks
- **Intensity:** 65-75% of target heart rate.
- **Duration:** 40 minutes per session. Patients will be instructed to follow low fermentable short chain carbohydrates diet (low FODMAP) intervention for 12 weeks limiting daily fermented carbohydrate and dairy products intake and increase intake of protein, whole grains, fruits and vegetables

(Appendix V)

- **Group B**

Patients will receive high intensity interval training (HIIT)

The program will be in form of: **(Clark et al.,2020).**

- **Frequency:** High intensity interval training will be scheduled 3 times per week for 12 weeks
- **Intensity:** 90% of target heart rate including 10 bouts of 1 minute interspersed with 10 bouts of 1 minute of active recovery 50% of target heart rate.
- **Duration:** the session will last 30 minutes includes warming up and cooling down periods

Patients will be instructed to follow low fermentable short chain carbohydrates diet (low FODMAP) intervention for 12 weeks limiting daily fermented carbohydrate and dairy products and increase intake of protein, whole grains, fruits and vegetables

Group C

Patients will be instructed to follow low fermentable short chain carbohydrates diet (low FODMAP) intervention for 12 weeks limiting daily fermented carbohydrate and dairy products and increase intake of protein, whole grains, fruits and vegetables **(Vareny et al.,2017).**

Only the patients who will attend > 80% of the exercise training sessions will be included in this study.

Data Analysis and statistical design

- The collected data was analyzed using the statistical program SPSS ver. 20.0.
- The mean and standard deviation were calculated for all measured variables.
- Pearson correlation coefficient was used to determine the relationship between the measured variables.
- Statistical significance was set at $p < 0.05$.

REFERENCES

Aziz I & Simrén M (2021). The overlap between irritable bowel syndrome and organic gastrointestinal diseases. *The Lancet Gastroenterology & Hepatology*, 6(2), 139–148.

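### N=66 gives 80% power only if almost all 66 patients are analysed; the attendance rule removes randomised patients, from the two exercise groups only, and no loss is allowed for

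*Combined protocol and SAP*

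**What the plan says.** Chapter III, Patients, gives the aim of the calculation as "To detect a large effect size of 0.4 with power of 80" per cent, at α=0.05, and concludes that "the required sample size required for this study was $N=66". It names no statistical test. The same chapter states "Patient will be randomly assigned to three groups", and of each group it says "This group will include 22 patients with IBS". Three groups of 22 use up all 66, so the number enrolled equals the number required.

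At the end of the Management procedure section the plan adds: "Only the patients who will attend > 80% of the exercise training sessions will be included in this study". Groups A and B train three times a week for 12 weeks; group C receives the diet plan alone.

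The only statement bearing on losses is under Basic Assumptions in Chapter I: "All patients will stick to the program and will follow instructions". Neither document part gives an expected loss rate, an allowance for losses, a replacement rule, an analysis population based on randomisation, or a method for missing data. The Data Analysis section lists means, standard deviations, Pearson correlation and a 0.05 significance level, and names no between-group test.

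**The concern.** The power statement needs close to 66 analysed patients, while the attendance rule provides for analysing fewer. The sample size rests on full adherence; the inclusion rule anticipates that some patients will not adhere.

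Two things are at stake. First, the plan's hypothesis is that the two training programmes do not differ significantly, and the declared purpose of the calculation is to guard against a type II error. A non-significant result would be read as support for the hypothesis, so a power figure that can erode unnoticed matters more than usual. Second, a patient's attendance is determined after allocation and may well be related to fitness, symptoms or tolerance of the assigned programme. Removing low attenders from A and B, but never from C, means the groups analysed are no longer the groups that were randomised. This is a bias issue, and it remains even when the number removed is too small to affect power.

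**Working it through.** **Inputs.** Effect size 0.4, power 80%, α=0.05, N=66, three groups of 22 (Chapter III, Patients). Scheduled sessions: 3 × 12 = 36 (Management procedure). No loss rate is given, so every loss level below is an assumption. Reading 0.4 as Cohen's f in a one-way ANOVA is an inference, tested in step 1.

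**Step 1: reproduce 66.** For the omnibus F test with three equal groups,

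Power = 1 − G(Fcrit; 2, N−3, λ), with λ = f²N = 0.16N,

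where G is the noncentral F distribution function and Fcrit the central 95% point. At N=66, λ = 0.16 × 66 = 10.56, Fcrit(2, 63) = 3.143 and power is 81.8%. The next smaller balanced size, 63, gives 79.8%. So 66 is the smallest balanced N that reaches 80%. Other readings do not give 66: two groups with d=0.4 need 198 (two-sided) or 156 (one-sided), d=0.8 needs 50, and a correlation of 0.4 needs 47.

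**Step 2: what the attendance rule requires.** 0.80 × 36 = 28.8, so a patient must attend at least 29 sessions, and one who attends 28 or fewer is removed. The rule can act on 22 + 22 = 44 of the 66 patients.

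**Step 3: losses spread roughly equally over the groups, f=0.4.**

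| Analysed N | λ = 0.16N | Power |
|---|---|---|
| 66 | 10.56 | 81.8% |
| 64 | 10.24 | 80.5% |
| 63 | 10.08 | 79.8% |
| 61 | 9.76 | 78.3% |
| 60 | 9.60 | 77.6% |
| 54 | 8.64 | 72.6% |

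The margin is two patients; the third loss takes power below 80%.

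**Step 4: losses in A and B only.** With unequal groups the result depends on which means differ. Fix the true means (SD 1) so that f=0.4 under equal allocation, and use λ = Σ nᵢ(mᵢ − m̄)², with m̄ weighted by nᵢ. Two patterns bound the range:

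- A and B at opposite extremes, C midway (A +0.490, B −0.490, C 0). With equal A and B sizes, λ = (n_A + n_B) × 0.24.
- A and B equal, C apart by 0.849. Then λ = [(n_A + n_B) × n_C / N] × 0.72.

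| A/B/C | λ, A and B extremes | Power | λ, C apart | Power |
|---|---|---|---|---|
| 21/21/22 | 42 × 0.24 = 10.08 | 79.8% | (42 × 22/64) × 0.72 = 10.40 | 81.1% |
| 19/19/22 | 38 × 0.24 = 9.12 | 75.3% | (38 × 22/60) × 0.72 = 10.03 | 79.5% |
| 16/16/22 | 32 × 0.24 = 7.68 | 67.1% | (32 × 22/54) × 0.72 = 9.39 | 76.3% |

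The lowest values arise when A and B differ most, which is the contrast named in the hypothesis.

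**Step 5: effect of keeping low attenders in.** If analysing all 66 dilutes the effect, power also falls: at N=66, f=0.38 gives 77.5% (λ = 0.1444 × 66 = 9.53) and f=0.36 gives 72.6% (λ = 0.1296 × 66 = 8.55). These values of f are illustrative.

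**The case against.** The sample-size arithmetic is right: 66 is what the stated inputs give, and a missing allowance is an omission rather than a wrong number. That stands. A reader might infer that the figure of 66 is itself in error, and the documents do not support that.

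A reader might also infer that the trial will not have 80% power. That needs a loss rate, and none is given. If nobody is lost, power is 81.8%; with five losses spread over the groups it is still 78.3%. The plan also discloses full adherence as an assumption. This stands too, and it limits the point to power that is unprotected rather than power known to be missing.

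The wording does not exclude replacing low attenders until each group reaches 22. It does not provide for it either, and replacement would restore the number while leaving groups A and B selected on attendance.

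The ANOVA is inferred from a numerical match, and omnibus power does not describe the comparison of A with B that the hypothesis names. Both remarks are fair. The first is a reason for the plan to name its test; the second means that the figures here say nothing directly about that pairwise contrast.

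Finally, analysing everyone does not secure 82%, because low attenders may dilute the effect (step 5). That is a real cost of the fix, but it does not justify selecting patients after randomisation.

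**Conclusion.** The point holds in this form: the stated 80% power is not protected, and the attendance rule introduces post-randomisation selection confined to groups A and B. The margin is two patients when groups stay roughly equal. When losses fall only in the exercise groups, one loss in each can already take power to 79.8% under the least favourable pattern of means; the ranges are 75–79% at 19/19/22 and 67–76% at 16/16/22.

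These figures rest on the inferred omnibus ANOVA, on f=0.4, and on assumed loss levels. The selection problem rests on none of them; it follows from the wording of the rule and from group C having no sessions. With small losses the power cost is a few points, so this should be corrected but does not invalidate the design.

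**What to change.** No additional enrolment is needed.

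1. Replace the attendance rule in the Management procedure section. The primary analysis includes every randomised patient with a week-12 measurement, in the group assigned. The subset with more than 80% attendance is a sensitivity analysis only.
2. In the sample-size paragraph, name the test and make the power conditional, for example: 66 patients give 82% power for the three-group omnibus test at f=0.4 if all are analysed; with losses in the exercise groups only, about 75–79% at 19/19/22 and 67–76% at 16/16/22, depending on the pattern of means. Label the loss levels as assumptions. The Data Analysis section should name the same test.

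Cost: the attendance rule and the power sentence are reworded, with a matching line in the Data Analysis section. The stated power becomes less favourable, and including low attenders may dilute the estimated effect somewhat. In return, the primary comparison follows the randomisation and the analysed number stays as close to 66 as the data allow.

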Moderate aerobic exercise affects the intestinal system mainly through gut immune function, gut barrier integrity, as well as gut motility, intestinal pH and gut hormones release; and bile acids metabolism within enterohepatic circulation (**Resende et al., 2021**).

Also High-intensity interval training is a popular, time-efficient mode of exercise to improve metabolic health and aerobic fitness, both of which have been associated with healthier gut bacterial community structure (**Rettedal et al., 2020**).

Statement of the Problem:

Is there a significant difference between the effect of moderate continuous versus high interval intensity training on gut dysbiosis and glucagon like peptide hormone in irritable bowel syndrome?

The Purpose of the Study:

To compare the effect of moderate continuous versus high interval intensity training on gut dysbiosis and glucagon like peptide hormone in irritable bowel syndrome.

Significance of the Study:

Irritable bowel syndrome affects around 11% of the global population with variation by geographic region: the highest in South America (21.0%) and the lowest occurring in South Asia (7.0%). In Egypt, the prevalence was 34% in primary healthcare center attendees. IBS significantly reduces work productivity and health-related quality of life (**Mohamed et al.,2021**).

The quality of life for patients suffering from IBS is greatly affected physically, psychologically, and economically. Several cases reported difficulties in concentration, decreased energy level, and lower self-esteem. In-addition IBS is

inducing occupational hazards as it affects the performance of patients at their jobs (**Elsayed et al.,2021**).

Although half of the cases referred to gastroenterologists is due to IBS, no clear etiology was found; however, some researches revealed that certain factors such as psychological factors, dietary habits, and exercise level were related to IBS onset and course (**Elhosseiny et al.,2019**).

Previous studies have been done separately on the effect of moderate intensity continuous training program and high intensity interval training on irritable bowel syndrome and gut dysbiosis, it is rational to compare between two training programs to know which is more effective to improve gut microbiota balance.

Delimitations:

This study will be delimited to the following aspects:

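### GLP-1 is a primary outcome in obese patients with prediabetes, yet no exclusion covers glucose-lowering or GLP-1-acting drugs, and the aim does not name this population

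*Combined protocol and SAP*

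**What the plan says.** All references are to the combined protocol and SAP.

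**Outcomes.** The list of outcomes in Chapter III names two primary outcomes: faecal short-chain fatty acids (SCFAs) and GLP-1 measured by ELISA.

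**Eligibility.** Under Inclusion criteria in Chapter III, item 2 is "Body mass index (BMI) will range from 30 to 34.9" kg/m², item 4 is "Prediabetic with glycated hemoglobin HbA1c of 5.7 – 6.4", and item 5 is "Sedentary subjects with daily steps count less than five thousand steps measured by pedometer". The twelve exclusions include antibiotics or probiotics in the last two months. None mentions glucose-lowering drugs, drugs acting on GLP-1, or other medication.

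**Population in the aims.** The Purpose of the Study reads "To compare the effect of moderate continuous versus high interval intensity training on gut dysbiosis and glucagon like peptide hormone in irritable bowel syndrome". The Hypothesis begins "It will be hypothesized that there will be no significant difference between the moderate continuous versus high interval intensity training on gut dysbiosis" and also ends with IBS, unqualified. The Statement of the Problem and the opening aim of Chapter III do the same. The Patients section says "This study will be carried out on sixty six irritable bowel syndrome patients of both sexes" and adds only the age range.

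**The earlier list.** The Delimitations section opens with "Subjects will be delimited to patients with irritable bowel syndrome selected from the outpatient of national nutrition institute with the following criteria". It gives both genders, age 20 to 45, "Their Body mass index ranged from 30 to 34.9", and four exclusions. It does not mention HbA1c or step count.

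**The concern.** The plan guards one primary outcome against drug interference and leaves the other open. Antibiotics and probiotics could disturb the gut flora that produce SCFAs, and recent users are excluded. Nothing equivalent protects GLP-1, although enrolment is confined to patients with obesity and raised HbA1c, where use of glucose-lowering or GLP-1-acting drugs is a reasonable thing to ask about. With 22 patients per arm, a handful of users can widen the spread of GLP-1 or, by chance, fall mostly in one arm. The plan has no rule for recording such use, so neither effect could be recognised afterwards.

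The second matter is one of wording. A reader of the purpose and hypothesis would take the result to concern people with IBS generally. The patients studied are sedentary adults with IBS, BMI 30 to 34.9 and HbA1c 5.7 to 6.4. The HbA1c condition appears once, without a reason, and HbA1c is neither an outcome nor a covariate.

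**Working it through.** **1. Reproduce the plan's sample size.** Inputs from the sample-size paragraph of Chapter III: effect size 0.4, called large; power 80%; α = 0.05; N = 66. Three groups of 22 come from the group descriptions. The test is not named. Reading 0.4 as Cohen's f in a one-way ANOVA, the noncentrality is λ = f² × N = 0.16 × 66 = 10.56 on 2 and 63 degrees of freedom, and power is 0.818. N = 63 gives 0.798, so 66 is the smallest balanced total that reaches 80%. The plan's figure is reproduced.

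**2. Can a user of such a drug enter?** Each Chapter III criterion was compared with a patient who has prediabetes and takes a glucose-lowering or GLP-1-acting drug.

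| Criterion | Bars this patient? |
|---|---|
| Age, BMI, IBS symptoms, step count | No |
| Prediabetes with HbA1c in range | No |
| Antibiotics or probiotics in the last two months | No, other drugs |
| The other eleven exclusions | No, none concerns medication |

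The answer is yes. A medical history is foreseen for every patient under Basic Assumptions, but no rule acts on what it shows.

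**3. Size, as an illustration.** The documents give neither the rate of use nor the effect of a drug on the measured value. Assume m users in each arm of 22, each with GLP-1 shifted by s SD, and f = 0.4 expressed in the SD of non-users. With p = m/22, the within-arm variance becomes v = 1 + s² × p(1 − p), and the effective effect size is 0.4/√v.

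| s (assumed) | m per arm (assumed) | v | Effective f | Power at N = 66 |
|---|---|---|---|---|
| none | 0 | 1.000 | 0.400 | 0.818 |
| 1 SD | 1 | 1.043 | 0.392 | 0.800 |
| 1 SD | 2 | 1.083 | 0.384 | 0.785 |
| 1 SD | 3 | 1.118 | 0.378 | 0.771 |
| 2 SD | 1 | 1.174 | 0.369 | 0.749 |
| 2 SD | 2 | 1.331 | 0.347 | 0.692 |
| 2 SD | 3 | 1.471 | 0.330 | 0.645 |

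Example for s = 2, m = 1: p = 1/22 = 0.0455; p(1 − p) = 0.0434; v = 1 + 4 × 0.0434 = 1.174; f = 0.4/1.083 = 0.369.

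**4. Chance imbalance.** One user more in one arm than in another moves the difference in means by s/22: 0.05 SD at s = 1 and 0.09 SD at s = 2. Three more would move it by 0.14 SD or 0.27 SD. For comparison, the standard error of a difference between two arms of 22 is √(2/22) = 0.30 SD. Under randomisation the expected imbalance is zero, and its random part is what the extra variance in step 3 already represents. The two should not be added together.

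**5. Wording of the population.** Set beside the inclusion criteria, the problem, purpose, hypothesis and aim lack three restrictions: BMI, HbA1c and step count. The same restrictions apply to all three randomised arms, so they do not affect the between-arm contrast. Naming them changes neither N nor power under the stated standardised effect size.

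**The case against.** The strongest reply is that this is ordinary generalisability plus a gap that nobody has shown to matter. Every patient must meet an IBS criterion, all arms share the same restrictions, and randomisation balances drug use in expectation. A narrow, untrained sample is a defensible choice. The rate of use and the effect on this assay lie outside the documents. All of that stands, and it is why the point is a modest one. It does not close the gap in medication: randomisation removes systematic bias but not added variance, and at present nothing would be recorded.

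Four stronger readings are tempting, and the documents do not support them.

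- *The GLP-1 answer does not match the objective.* A shared restriction does not bias the comparison, nothing in the documents shows that the training effect varies with HbA1c, BMI or step count, and the plan contains no conclusion section that overreaches.
- *The two eligibility lists conflict.* Chapter III repeats every eligibility item in the Delimitations and adds more. It contradicts none, and BMI stands in both.
- *A patient with treated diabetes and HbA1c back in range meets every criterion.* Item 4 requires the patient to be prediabetic as well as in range, which argues against admission.
- *The trial speaks for only a small percentage of IBS patients.* The documents give no rates from which such a share could be computed.

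**Conclusion.** The concern holds in a limited form. As written, the plan admits patients with prediabetes who take drugs that may act on one of its two primary outcomes, while it excludes recent antibiotics and probiotics. The likely consequence is extra variance in GLP-1, or a chance imbalance at 22 per arm, rather than systematic bias. Its size is unknown. The illustrated powers, from 0.80 down to 0.64 against 0.82, rest wholly on an assumed one to three users per arm, an assumed shift of 1 or 2 SD, and the reading of 0.4 as Cohen's f. If few or no users enrol, the loss is negligible.

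The unqualified wording of the problem, purpose, hypothesis and aim limits what the result can be said to show. It leaves the comparison itself intact. The opening of the document was not available for this review, so any qualification given there could not be checked.

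This is a cheap improvement, not a defect that undermines the trial.

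**What to change.** 1. Add to the Chapter III exclusion criteria the current use of glucose-lowering or GLP-1-acting drugs. Record any such drug started during the 12 weeks. This is an eligibility and data-recording rule only; no patient's treatment is changed.
2. In the problem, purpose, hypothesis and Chapter III aim, state the population as sedentary adults with IBS, BMI 30 to 34.9 and HbA1c 5.7 to 6.4, and give the reason for the HbA1c condition.
3. Have the Delimitations section refer to the Chapter III criteria, so that one list governs. This is clerical.

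The cost is a few screened patients not enrolled, one more item on the case record form, and a narrower stated claim. N = 66 is unaffected.
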